1.1 Primary objectives

- 1.1.1 To determine treatment efficacy defined as histologic regression to CIN 1 or less at weeks 20-24 (4 to 8 weeks after the end of imiquimod treatment) in the HPV Vaccine + Imiquimod group compared to control
- 1.1.2 To determine treatment efficacy defined as histologic regression to CIN 1 or less at weeks 20-24 (4 to 8 weeks after the end of imiquimod treatment) in the Imiquimod group compared to control

1.2 Secondary objectives

- 1.2.1 To assess complete regression (i.e., histologic remission) at weeks 20-24 (4 to 8 weeks after the end of imiquimod treatment) in each group
- 1.2.2 To assess HPV clearance in each group
- 1.2.3 To assess treatment tolerability

1.3 Exploratory/correlative objectives

- 1.3.1 To assess T cell infiltration in post-treatment cervical biopsies and endocervical cytobrush samples
- 1.3.2 To assess HPV16 E7 immunity in CD4/CD8 T cells

HIC#: 1603017415 Protocol version 11.0

CIN 2/3

2.0 BACKGROUND AND RATIONALE

Human papillomavirus (HPV) infection, which is sexually transmitted, leads to a wide range of conditions in women from genital warts and precancerous cervical dysplasia to cancers of the genital tract and elsewhere. Globally, 9 million cases of precancerous high-grade "cervical intraepithelial neoplasia (CIN 2/3) are detected annually through cervical cancer screening programs; 330,000 in the U.S. alone.¹ Persistent infection with oncogenic ("high-risk") HPV types is one of the most important risk factors for development of CIN 2/3 which poses significant risk of progression to invasive cervical cancer.²-⁴ In order to prevent this progression to invasive cancer, CIN 2 and 3 lesions require frequent surveillance and management through serial pelvic exams, cytology, colposcopy-directed biopsies, and various invasive procedures, including cervical ablation or excision that can negatively impact future pregnancies. Surveillance is often complicated by poor compliance, significant stress and anxiety, and low tolerance for serial pelvic exams and procedures. In addition, the direct medical costs in the U.S. associated with both screening for and treating HPV-associated diseases is estimated to be \$8.0 billion dollars, over 80% of which is for routine cervical cancer screening and follow-up.⁵

Current FDA-approved prophylactic HPV vaccines have not shown therapeutic effect in patients with pre-existing HPV-associated cervical lesions. 6-8 Treatment options for CIN 2-3 involve a variety of destructive or excisional procedures, although in the U.S. excision is generally favored in these women at higher risk of invasive cervical cancer as it allows for pathologic evaluation of the specimen for diagnosis and for evaluation of surgical margins. Ablation techniques typically utilize cryotherapy or laser while excision techniques include scalpel, electrosurgery or laser.

A major concern with the destructive or excisional treatment modalities currently available for CIN 2-3 include future obstetric risk (pregnancy loss, preterm premature rupture of membranes, and preterm delivery) and cervical stenosis, or narrowing of the cervical canal, which can result from scarring after treatment. The risk of cervical stenosis after an excision procedure was shown to be 7% in one study and this can have several negative outcomes including difficulty with normal cervical dilation during labor, difficulty with common office procedures (e.g., endometrial biopsy), and might impede normal menstrual flow. One large population-based study found that women who gave birth after a cervical excision procedure were significantly more likely to have a preterm delivery and had a significantly higher risk of a late abortion (< 24 weeks gestation) compared with women who gave birth prior to the surgical excision. One content is the surgical excision.

Given these circumstances, precancerous cervical dysplasia is an ideal candidate for therapeutic vaccination to clear CIN 2-3 without destroying cervical tissue. Previous attempts at developing vaccines that mount systemic cellular immunity responses against other viral sexually transmitted infections have been unsuccessful. We believe that one of the problems in current therapeutic vaccine approaches is the lack of effector T cell migration to the sites of infection. Although systemic memory T cells can gain entry to certain organs, other anatomic locations including the vagina are immunologically restrictive and prevent entry of memory T cells. Inflammation or infection is often needed to permit entry of systemically circulating activated T cells into restrictive tissues to establish tissue-resident memory T cells. 14-17

Our group has recently reported a highly effective vaccination strategy ("prime and pull") to establish tissue-resident memory T cells in the genital tract. ¹⁸ An initial systemic T cell response is triggered ("prime") by parenteral vaccination. Activated T cells are then recruited into the genital mucosa ("pull") through the application of specific chemokines to the restrictive genital tract and then establish a long-term tissue-resident memory T cell (T_{RM}) pool and mediate protective immunity. ¹⁴ In HIC#: 1603017415

Protocol version 11.0

CIN 2/3 3

mice, this strategy reduces spread of infectious viruses and prevents clinical disease. These results strongly suggest the possibility of inducing T cell responses against oncogenic HPV genotypes through immunization with a prophylactic HPV vaccine, followed by recruitment of HPV-activated T cells into cervical lesions using a local immune-response modulator.

Imiquimod, a topical immune response modulator, has antiviral and antitumor activity, induces cytokines including interferon, tumor necrosis factor, and interleukins 1, 6, and 8, and activates T cells triggering an immune response associated with HPV clearance. Indicate Image Image

We believe that "prime and pull" will provide further protection to imiquimod treatment alone, by eliciting robust T cell responses that can be pulled into the genital mucosa using chemokines induced by imiquimod application. Currently, a 9-valent prophylactic HPV vaccine (9vHPV) is commercially available and provides protection against 7 high-risk HPV types that cause 90% of all cervical cancers (and protects against 2 additional HPV types that cause 90% of all genital warts). ²² 9vHPV is a sub-unit protein vaccine; vectors expressing the papillomavirus *L1* gene have been used to generate virus like particles (VLPs) that mimic the wild type virus capsid morphologically and antigenically but contain no DNA and are therefore noninfectious. This vaccine is highly immunogenic, inducing a robust serum neutralizing antibody response which prevents incident infection. ^{25,26} Previous studies have demonstrated induction of antigen-specific T cell responses by prophylactic HPV vaccines as well. ²⁷⁻³⁰

Published treatment efficacy with imiquimod²⁴ and the preclinical in vitro data presented above and fully reported in *Nature*¹⁸ clearly suggest that a "prime and pull" vaccination strategy may provide significant therapeutic effect for HPV-associated CIN 2/3 lesions. Because the development of a novel, effective treatment modality without the need of destructive interventions on the cervix in CIN 2/3 remains an unmet medical need, in this study we are planning a multi-arm randomized clinical trial to determine the therapeutic clinical effect and resulting immune response of a "prime and pull" method of treatment in women with CIN 2-3 lesions using imiquimod vaginal suppository in conjunction with the commercially available 9-valent HPV vaccine.

3.0 SUBJECT ELIGIBILITY AND EXCLUSIONS

3.1 Eligible Subjects:

HIC#: 1603017415 Protocol version 11.0

- 3.1.1 Subjects must have untreated cervical biopsy-proven, CIN 2/3 ectocervical lesion(s).
- 3.1.2 Subjects must have satisfactory colposcopy with visualization of the entire transformation zone or a negative endocervical curettage if colposcopy is unsatisfactory.
- 3.1.3 Subjects must be high-risk HPV+ as determined by commercially available DNA hybridization test which tests for 13 high-risk HPV types.
- 3.1.4 All Subjects must have a histologic diagnosis of CIN 2,3 cervical lesion(s) confirmed by a study pathologist.
- 3.1.5 Subjects must have signed an approved informed consent.
- 3.1.6 Subjects of childbearing potential must have a negative urine pregnancy test within 7 days prior to the study entry and be practicing an effective form of contraception.
- 3.1.7 Subjects must be at least 18 years of age based on previous and current cervical cancer screening guidelines.
- 3.1.8 Subjects must be fluent in speaking English or Spanish.
- 3.2 Ineligible Subjects:
- 3.2.1 Subjects with unsatisfactory colposcopy* (unable to visualize entire transformation zone) or evidence of endocervical disease defined as CIN 2/3 diagnosed on endocervical curettage. *Subjects with unsatisfactory colposcopy but negative endocervical curettage are eligible (see 3.1.2).
- 3.2.2 Subjects with a history of invasive cervical cancer
- 3.2.3 Subjects with a history of other invasive malignancies, with the exception of non-melanoma skin cancers are excluded if there is any evidence of other malignancy being present within the last five years. Subjects are also excluded if their previous cancer treatment contraindicates this protocol therapy.
- 3.2.4 Subjects with any unstable medical issue (including cardiac issues as above, active treatment for pulmonary embolism, CVA, renal or hepatic insufficiency, active infection/sepsis requiring IV antibiotics).
- 3.2.5 Subjects who have an uncontrolled seizure disorder, or active neurological disease.

HIC#: 1603017415 Protocol version 11.0

- 3.2.6 Subjects known to be seropositive for HIV and active hepatitis, even if liver function studies are in the normal range. Subjects otherwise immunocompromised will also be excluded (chronic steroid use, taking immunosuppressive medications).
- 3.2.7 Pregnant or breastfeeding subjects.
- 3.2.8 Subjects who have had a total hysterectomy (removal of uterus and cervix) or trachelectomy (removal of cervix).
- 3.2.9 Subjects with a known hypersensitivity to imiquimod. Subjects with a known hypersensitivity to any prophylactic HPV vaccine or severe allergic reactions to yeast (vaccine component).
- 3.2.10 Subjects who have received their first dose of HPV vaccine < 4 weeks ago or their second dose < 12 weeks ago.
- 3.2.11 Known hypersensitivity or prior intravaginal treatment with Imiquimod
- 3.3 Inclusion of Minorities:
- 3.3.1 As men do not have uteri, only women will be enrolled in this trial. Women fluent in English or Spanish will be eligible for study enrollment based on limited resources in providing appropriate informed consent and research follow up to subjects only fluent in other non-English or Spanish languages. We will not exclude potential subjects from participating in this or any study solely on the basis of socioeconomic status. Every attempt will be made to enter all eligible subjects into this protocol and therefore address the study objectives in a broad population of women with high-grade cervical dysplasia.

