6.0 TREATMENT PLAN AND ENTRY PROCEDURE/REGISTRATION PROCEDURE

HIC#: 1603017415 Protocol version 11.0

6.1 Study Entry: Subjects will be screened and consented by the P.I. or a member of the study staff. Consent may be obtained remotely. The consent form can be mailed or emailed to the research participant who will sign a printed version of the consent form and fax/scan/email/send a picture of the signed consent form or mail the signed consent form back to the researcher.

[figure not shown]

FIGURE 1: Study Timeline

6.2 Treatment Plan This is a randomized Phase II, three arm control trial in subjects with CIN 2/3 high grade cervical dysplasia. Subjects with CIN 2/3 meeting eligibility criteria will have cervical biopsy specimens centrally reviewed by study pathologist to confirm diagnosis. HPV DNA test and HPV 16/18 genotyping will be performed from endocervical cytobrush samples to determine HPV status associated with the dysplasia.

Subjects who have CIN 2/3 with HPV+ disease will be enrolled in this study. Subjects will be randomized to one of three arms: observation only (control), imiquimod only, imiquimod + 9-valent HPV vaccine. All cytology and cervical biopsy specimens related to the study will be centrally reviewed by study pathologists who will be blinded to treatment assignment.

6.2.1 Pre-Treatment Visit/Study Enrollment: After the index cervical biopsy demonstrating CIN 2-3, all subjects will be brought back to clinic to discuss results and management. After obtaining informed written consent the following pre-treatment tests will be performed: medical history, physical exam with pelvic exam, vital signs, urine pregnancy test (must be performed within 7 days of treatment), translational blood

HIC#: 1603017415 Protocol version 11.0

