Vaginal suppositories will be self-applied by the subjects in the evening right after going to bed. Subjects will be advised not to have sexual intercourse during the nights in which they applied vaginal suppositories and to perform a vaginal douche in the morning. Subjects will be instructed to suspend the application of vaginal suppositories during the first 3 days of their menses. Subjects will be advised to keep the study medication refrigerated. In case of persistent side effects in subjects of the imiquimod group, the dose of the study medication will be modified and participants will receive vaginal suppositories containing only 50% of the original imiquimod dose (vaginal suppositories containing 3.125 mg imiquimod).

Missed doses of imiquimod can be made up the following day. Otherwise, the dose must be skipped and subjects should take the next scheduled dose at the usual time.

Imiquimod will be dispensed in boxes containing 18 vaginal suppositories (treatment weeks 1-8) at the beginning of the treatment course. During follow up visit at week 8 (see below), subjects will be provided a new box of 24 vaginal suppositories to complete treatment course for weeks 9-16. Study drug will be prescribed by the investigator and may be dispensed either by the investigator or study staff.

HIC#: 1603017415 Protocol version 11.0

CIN 2/3

11

(3) Imiquimod + HPV vaccine: At the baseline visit, this group will be instructed about the correct method of self-application of imiquimod 6.25mg as a vaginal suppository as described above, storage of medication, possible side effects. Subjects will be provided a diary and case report form to record vaginal suppository application and side effects will be recorded per NCI Common Terminology Criteria for Adverse Events (CTCAE 4.0). In addition, all women (regardless of age) will be administered a dose of the HPV vaccine on day of enrollment (regardless of previous HPV vaccination history). Women previously unvaccinated will receive an additional booster dose at 8 weeks. Local pain will be assessed with a visual analog scale immediately after vaccine administration and 5 minutes later. Subjects will be provided a separate case report form to record vaccine side effects per CTCAE 4.0.

Missed doses of imiquimod can be made up the following day. Subjects are encouraged to complete taking all prescribed doses. If additional time is required toward this goal of treatment, the scheduled dosing period may be extended.

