15.5 Analysis for the Primary Objective

The co-primary objectives of this study are to test superior treatment efficacy of Imiquimod + HPV vaccine (Trt1) compared to control (Trt0), and likewise Imiquimod only (Trt2) compared to control (Trt0). The primary outcome is *histologic regression* (yes/no) after completion of the 12 to 16 weeks imiquimod course. The full definition of *histologic regression* and how it is determined is described in Section 5.1.

The co-primary hypothesis tests are:

 $\{H_{01}: p_1 - p_0 = 0 \text{ versus } H_{11}: p_1 - p_0 > 0\}$ and

 $\{H_{02}: p_2 - p_0 = 0 \text{ versus } H_{12}: p_2 - p_0 > 0\}$

 p_0 , p_1 , and p_2 are the proportion of subjects on Trt0, Trt1, and Trt2, respectively, who are determined to have *histologically regressed*. Fisher's Exact Test will be used to assess if the data support rejecting the null hypothesis H_{01} , and likewise for H_{02} . To control Type I error, we will use a conservative Bonferroni adjustment for multiple comparisons with one-sided $\alpha = (0.05)/2 = 0.025$ as the significance level for each test. Rejection of a particular null hypothesis suggests superior efficacy of that specific treatment compared to control. Exact 95% confidence intervals will be calculated for p_1 - p_0 and for p_2 - p_0 . Confidence intervals for 'risk ratios' (p_1/p_0 , p_2/p_0) in addition to 'risk differences' (p_1 - p_0 , p_2 - p_0) may also be estimated. The main analysis will use the **modified ITT analysis set**. Sensitivity analyses for the same statistical method using the **modified ITT completers** and/or **per protocol analysis sets** may also be provided.

HIC#: 1603017415 Protocol version 11.0

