15.7 Exploratory/Correlative Objectives

To characterize the association of **T cell infiltration** into the cervical dysplasia (i.e. frequencies and anatomical distributions of CD4 and CD8 T cells within the CIN) and pre- and post-immune therapy responses to HPV16/18 E7 antigens in subject peripheral blood lymphocytes (PBL) and serum with **clinical outcomes** (histologic regression/remission) and **viral clearance**. T_{RM} frequencies ,distributions and responses will be measured within subjects (pre and post 'prime and pull'), and changes from baseline will be compared between the treatment groups at relevant time points. Descriptive summary statistics will be used to evaluate associations and ANOVA will be the used to test the statistical significance of associations. The main analysis will use the **modified ITT analysis set**. Sensitivity analyses for the same statistical method using the **modified ITT completers** and/or **per protocol analysis sets** may also be provided.

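### Previously HPV-vaccinated women can enter every arm, but sections 15.5 to 15.7 never use vaccination history, so the between-arm T-cell comparison and any indirect reading of the vaccine's contribution are blurred

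*Combined protocol and SAP*

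**What the plan says.** Eligibility is decided before randomisation. On prior vaccination, section 3.2.10 excludes only "Subjects who have received their first dose of HPV vaccine < 4 weeks ago or their second dose < 12 weeks ago". Section 6.2 then states: "Subjects will be randomized to one of three arms: observation only (control), imiquimod only, imiquimod + 9-valent HPV vaccine". No stratification factor is named.

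In the vaccine arm (section 6.2.1), every woman is dosed at enrolment whatever her vaccination record, and history decides the second dose: "Women previously unvaccinated will receive an additional booster dose at 8 weeks". Previously vaccinated women in that arm therefore receive one trial dose and the others two.

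The rationale (section 2.0) says of priming: "Previous studies have demonstrated induction of antigen-specific T cell responses by prophylactic HPV vaccines as well". It expects that the combined strategy "will provide further protection to imiquimod treatment alone, by eliciting robust T cell responses that can be pulled into the genital mucosa".

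Sections 15.5 and 15.6 compare each active arm with control, by Fisher's exact test and exact intervals for regression, and by exact intervals for remission and HPV clearance. Section 15.7 is where the active arms are set side by side: "changes from baseline will be compared between the treatment groups at relevant time points", with ANOVA as the test. None of these sections names vaccination history as a stratum, covariate or subgroup. Section 15.4 summarises baseline measures by arm but lists no individual variables.

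**The concern.** On the protocol's reasoning, a woman vaccinated some years ago and given imiquimod alone may receive both components: the prime earlier and the pull now. The imiquimod-only arm would then be a mixture of unprimed women and women who resemble the combination arm. The combination arm is itself a mixture of one-dose and two-dose women.

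Section 5.3.1 makes it the main translational aim to learn whether the combination establishes tissue-resident memory T cells. If the T-cell changes in the two active arms look alike, the vaccine may have added nothing, or the comparator may have been partly primed already. The plan contains no analysis that would help tell these apart, and a vaccination breakdown chosen after seeing the data would carry little weight.

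**Working it through.** **1. Where history is needed and where it is used.** It must be known for every woman to apply section 3.2.10, and in the vaccine arm to apply the week 8 booster rule. Sections 15.5, 15.6 and 15.7 do not mention it. Both halves of the point therefore stand on the text.

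**2. The plan's own figure.** Inputs from section 15.8: control rate 0.28, effect +0.35 (so 0.28 + 0.35 = 0.63), 38 women per arm, one-sided alpha 0.025. Enumerating two binomials and applying the one-sided Fisher test to each outcome gives power 0.8269. This matches the operating-characteristics table, as does the actual alpha of 0.0147 at zero effect. The plan assumes +35 points for both active arms, so it was not sized for any difference between them.

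**3. Bound on the dilution.** Let b be the response to imiquimod in unprimed women, d the gain from priming, f the previously vaccinated share, and k the fraction of the priming gain that earlier vaccination still provides (0 to 1). Suppose that a trial dose brings every woman to the full gain.

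- Imiquimod only: b + f x k x d
- Combination: b + d
- Visible difference: (1 - f x k) x d

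The documents give none of f, k or d. As an illustration, assume f = 20% to 60% and d = 20 points:

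| k | Visible difference at f = 20% | At f = 60% |
|---|---|---|
| 1 (full, durable earlier priming; re-dosing adds nothing) | 0.8 x 20 = 16 | 0.4 x 20 = 8 |
| 0.5 | 0.9 x 20 = 18 | 0.7 x 20 = 14 |
| 0 (earlier priming lost) | 20 | 20 |

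The first row is the bound: a loss of f x d, here 4 to 12 points. With d = 0, which the equal planned effects imply, the loss is zero.

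**4. What never-vaccinated women could show.** With the same f, they number 38 x 0.8 = 30.4 down to 38 x 0.4 = 15.2 per arm. Exact one-sided Fisher power at 0.025:

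| Women per arm | 28% vs 63% (active vs control) | 63% vs 83% (between active arms, d = 20) |
|---|---|---|
| 38 | 83% | 42% |
| 30 | 71% | 32% |
| 15 | 32% | 12% |

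For 63% vs 83%, the approximate 95% half-width, 1.96 x sqrt[(0.63 x 0.37 + 0.83 x 0.17)/n], is 19, 22 and 31 points for n = 38, 30 and 15.

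**5. Chance imbalance.** Under simple randomisation with 38 per arm, two arms differ by 15 points or more in vaccinated share with probability 11%, 17% or 21% when the true share is 20%, 30% or 50% (also assumed values). This is a reason to tabulate the share by arm.

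**The case against.** A reader might infer that the imiquimod-versus-control effect is overstated. The documents do not support that. Vaccinated women are expected equally in both arms, so the contrast is unbiased for the eligible population with type I error intact, and section 3.3.1 aims at a broad population. The 4 to 12 points are an excess only relative to a never-vaccinated estimand that the protocol does not adopt. This part of the objection stands in full.

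It is also true that no clinical test or interval between the active arms is planned, so for regression the blurring affects only an informal comparison of two results against control.

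A reader might also carry the factor 1 - f over to the T-cell contrasts. That is not shown. The vaccine is L1-based (section 2.0) whereas the blood assays measure E7 responses (section 5.3.2), and a change from baseline already removes part of any pre-existing circulating response. It would not remove recruitment into tissue after imiquimod, which is the mechanism proposed, so the concern remains for T-cell infiltration but without a number.

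Finally, section 15.4 names no baseline variable, so tabulating vaccination history is compatible with it, and small subgroups will not resolve a null result. Both points are right. They limit what the fix can achieve but do not supply the missing analysis.

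**Conclusion.** The point holds in a limited form. Earlier-vaccinated women are eligible in all arms, dose number in the vaccine arm depends on history, and no analysis in sections 15.5 to 15.7 takes account of either. The co-primary conclusions are not threatened. The exploratory T-cell comparison between arms, and any indirect inference about the vaccine's added value, are harder to interpret.

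The size cannot be stated from the documents. The reduction from 20 to between 16 and 8 points is an upper limit on dilution under assumed f and d, with full and durable earlier priming and no benefit from re-dosing. It should not be read as a consequence of the plan. That imiquimod-only women are partly primed is likewise an inference: it requires that vaccinated women enrol and that earlier vaccination still primes. This is an inexpensive improvement to the analysis plan; nothing in the primary analysis needs correcting.

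**What to change.** - **Section 15.4:** tabulate prior HPV vaccination (none/any) by arm.
- **Section 15.7:** include it as a factor in the ANOVA of T-cell changes. A main effect deals with imbalance but leaves the treatment contrast an average over both groups, so the next item is also needed.
- **Sections 15.5 and 15.7, supportive and descriptive only:** report in never-vaccinated women, next to the all-women results, the between-arm T-cell changes and the regression differences with confidence intervals for Trt1 minus control, Trt2 minus control and Trt1 minus Trt2. The last is the contrast that bears on the vaccine's contribution.

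The Fisher tests, their alpha, eligibility and treatment are unchanged. Section 15.1 already confines multiplicity adjustment to the primary analysis. The cost is a few sentences, since the history must be obtained for eligibility anyway. The drawback is imprecision, as the tables above show. The text should say in advance that these results cannot decide the meaning of a null finding by themselves.
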